9.4.2 Primary Endpoint Analysis

The primary endpoint will be the mean change from BC of the average daily OPP score during TRC3. The OPP will be calculated for each cycle as the total of OPP scores reported during the cycle divided by the number of days during the cycle in which the score was reported. For participants who discontinue early, their last cycle will be associated with the cycle number at entry into the cycle. The primary analysis will be conducted using the MFAS and will use a longitudinal model. The response vector for the model will be change from BC in the average OPP during TRC1, TRC2, and TRC3. Model terms will include the respective baseline, treatment, time (ie, cycle), and treatment-time interaction, allowing for the inclusion of individual outcomes over time (cycle). An unstructured error structure will be assumed. If

nonconvergence is encountered, compound symmetry (CS) and first-order autoregressive AR(1) error structures will be considered.

Least squares mean change from baseline for each treatment group, with corresponding standard errors will be provided. Estimated treatment differences (each active treatment group versus Placebo) with corresponding 95% CI and 2-sided p-values will also be provided for each active treatment group. No missing data will be imputed for the primary analysis.

Supportive analyses will be conducted using an analysis of covariance (ANCOVA) on the change from baseline to the TRC3, with treatment as a fixed factor and baseline OPP as a covariate.

The primary longitudinal and ANCOVA models will be repeated using the PP set.

A completers analysis will be performed for those participants who completed all 3 treatment cycles. Details regarding additional sensitivity and subgroup analyses of the primary efficacy endpoint will be described in the SAP.

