9.4.3 Secondary Endpoint Analysis

Secondary endpoints assessing change in continuous endpoints over time (either measurements within the cycle or at an individual visit) will use longitudinal models as described for the primary endpoint and/or ANCOVA models. Changes from SC to SFC will be compared using ANCOVA models in the SFAS. Select longitudinal models which focus on TRC1 and TRC2 may exclude TRC3 from the model. An unstructured error structure will be assumed for all longitudinal models. If nonconvergence is encountered, CS and AR (1) error structures will be considered.

Definitions corresponding to the incidence of clinically significant values will be provided in the SAP.

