#### 4.3. Sample Size

Approximately 760 pre-menopausal females aged 18 to 49 years old (inclusive), who have been surgically diagnosed with endometriosis within the last 4 months to 10 years prior to V1, will be screened to achieve 380 randomly assigned to the study treatment (95 participants in each group). A total of 380 participants will provide 84% power to detect a difference of 1 point between an OG-6219 dose group and Placebo in change from baseline to TRC3 of mean OPP, assuming a common SD of 2.2. This power calculation is based on a 2-sided test with Type I error of 0.05 and a dropout rate of 10%.

A minimum subset of 10 participants per group (~10%) will be enrolled for optional intensive PK sampling for the entire duration of the study.

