#### 8.3.5. Analysis of Primary Efficacy Endpoint

The primary endpoint will be analysed using a longitudinal model, i.e. a Mixed Models for Repeated Measures (MMRM), fitted to data from all participants with a post-treatment OPP measurement. The response vector for the model will be the change from BC in the mean OPP during TRC1, TRC2, and TRC3. Model terms will include the baseline cycle value (mean OPP for BC), treatment, time (i.e., cycle), and treatment-by-time interaction. An unstructured error structure will be assumed. If nonconvergence under the UN assumption is encountered a compound symmetry (CS) and autoregressive AR(1) error structures will be assumed in sequence. Estimated treatment differences (each OG-6219 treatment group versus

Placebo) with corresponding 95% CI and 2-sided p-values will be derived from the model for each treatment cycle.

Analysis using MMRM method will be implemented using the SAS® procedure MIXED as follows (example code only):

```
PROC MIXED DATA = ...;  
  CLASS CYCLE TREATMENT SUBJID;  
  MODEL CHG = BASELINE TREATMENT CYCLE TREATMENT*CYCLE /  
    DDFM=KR;  
  REPEATED CYCLE / SUBJECT = SUBJID TYPE=UN;  
  LSMEANS TREATMENT*CYCLE / PDIFF CL;  
RUN;
```

where CHG = change from baseline at each treatment cycle

TREATMENT = randomized treatment group (CCI BID, CCI BID, CCI BID, and placebo)

BASELINE = baseline cycle value

CYCLE = treatment cycle

SUBJID = subject ID

In addition, the mean OPP will be summarized by cycle and treatment group using descriptive statistics of observed data and change from baseline cycle values. Mean OPP by cycle will also be presented in listings.

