### 8.3.7. Supplementary Analyses for Primary Efficacy Endpoint

Two supplementary analyses will be performed for the MFAS, both using analysis of covariance (ANCOVA) models on the change from baseline to TRC3 with treatment as a fixed factor and baseline OPP as a covariate. In the first analysis, only subjects with data from TRC3 will be included. In the second analysis, subjects without data from TRC3 will have their TRC3 value imputed using last observation carried forward (i.e. the last available of the TRC2 and TRC1 values will be used.)

Estimated treatment differences (each OG-6219 treatment group versus Placebo) with corresponding 95% CI and 2-sided p-values will be derived from the model.

Analysis using an ANCOVA model will be implemented using the SAS® procedure MIXED as follows (example code only):

```
PROC MIXED DATA = ...;  
  CLASS TREATMENT;  
  MODEL CHG = BASELINE TREATMENT;  
  LSMEANS TREATMENT / PDIFF CL;  
RUN;
```

where CHG = change from baseline to TRC3

TREATMENT = randomized treatment group (CCI BID, CCI BID, CCI BID, and placebo)

BASELINE = baseline cycle value

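### If the unstructured fit fails, the fallback forces one variance on all three cycles, so the TRC3 standard error is mis-sized whenever TRC3 variability differs from earlier cycles

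*SAP*

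**What the plan says.** SAP 8.3.5 fits a mixed model for repeated measures: "The response vector for the model will be the change from BC in the mean OPP during TRC1, TRC2, and TRC3". The example code has "REPEATED CYCLE / SUBJECT = SUBJID TYPE=UN" with Kenward-Roger degrees of freedom and no empirical (sandwich) option. For failure of that fit, SAP 8.3.5 and Table 2 both state: "If nonconvergence under the UN assumption is encountered a compound symmetry (CS) and autoregressive AR(1) error structures will be assumed in sequence".

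The protocol names the same two structures without an order. Section 9.4.2 says that if "nonconvergence is encountered, compound symmetry (CS) and first-order autoregressive AR(1) error structures will be considered". The Synopsis repeats this, and 9.4.3 carries it to the secondary endpoints: "An unstructured error structure will be assumed for all longitudinal models", with the same two alternatives. SAP 8.4.3 and 8.5.3 reuse the 8.3.5 model for DYS, NMPP, dyspareunia, rescue medication and interference with daily activities.

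Neither document names a heterogeneous-variance structure or a robust standard error. None of the three sensitivity analyses in SAP 8.3.6 varies the covariance. SAP 8.3.7 plans supplementary ANCOVAs of change to TRC3; of these it says: "In the first analysis, only subjects with data from TRC3 will be included".

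**The concern.** UN lets each cycle have its own variance. CS and AR(1) each have two parameters, one of them a single variance shared by the three cycles. The primary hypothesis concerns TRC3 only, so under either fallback a model-based TRC3 standard error draws on a variance pooled over TRC1 to TRC3. If women vary more at TRC3 than earlier, the interval is too narrow and the test rejects too often. If they vary less, the interval is too wide and power is lost.

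Unequal variability is plausible, though undocumented. A cycle mean may rest on one daily score (SAP 8.3.3), and TRC3 alone is capped by a maximum treatment duration (SAP 8.3.3.1), so its means may rest on fewer days.

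The plan steps from the most flexible structure to two of the most restrictive. It passes over structures that keep a separate variance per cycle with fewer parameters than UN.

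**Working it through.** **Inputs.** From SAP 4.3: 95 per arm, SD 2.2 for change to TRC3, difference 1 point, two-sided 0.05, 10% dropout. From SAP 8.3.5: three cycles, hence 3×4/2 = 6 UN parameters. The TRC1 and TRC2 SDs are assumptions, because the documents give none.

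**Step 1: the plan's own figure.** SAP 4.3 states: "A total of 380 participants will provide 84% power to detect a difference of 1 point". Evaluable per arm: 95×0.9 = 85.5. SE = 2.2×√(2/85.5) = 0.336. Power = Φ(1/0.336 − 1.960) = Φ(1.012) = 84.4% (84.0% by noncentral t). It reproduces, so 2.2 serves as the TRC3 SD below.

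**Step 2: complete-data formula.** Write s1, s2, s3 for the cycle SDs. With a separate mean per arm and cycle, the TRC3 contrast is the difference of TRC3 arm means, and its true standard error is proportional to s3. CS replaces s3² by the average of the three variances. Hence

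- ratio r = √[(s1² + s2² + s3²)/3] / s3
- actual two-sided error = 2[1 − Φ(1.960 r)]

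This holds for CS; for AR(1) it is an approximation.

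| TRC1 / TRC2 / TRC3 SD | Mean variance | r | Actual error |
|---|---|---|---|
| 2.2 / 2.2 / 2.2 | 4.840 | 1.000 | 5.0% |
| 2.0 / 2.1 / 2.2 | 4.417 | 0.955 | 6.1% |
| 1.9 / 2.1 / 2.2 | 4.287 | 0.941 | 6.5% |
| 1.8 / 2.0 / 2.2 | 4.027 | 0.912 | 7.4% |
| 1.7 / 2.0 / 2.2 | 3.910 | 0.899 | 7.8% |
| 1.5 / 1.9 / 2.2 | 3.567 | 0.858 | 9.2% |
| 1.4 / 1.8 / 2.2 | 3.347 | 0.832 | 10.3% |
| 2.6 / 2.4 / 2.2 | 5.787 | 1.093 | 3.2% |

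In the falling case the cost is power: Φ(2.972 − 1.960×1.093) = Φ(0.83), about 80% instead of 84%.

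**Step 3: simulation with dropout.** REML fits, four arms of 95, 10% monotone dropout, correlations 0.75 between adjacent cycles and 0.6 between TRC1 and TRC3, no baseline term, critical value 1.96, 1,500 runs per setting (Monte Carlo standard error about √(0.05×0.95/1500) = 0.6 points).

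| TRC1 / TRC2 SD | CS: r, error | AR(1): r, error |
|---|---|---|
| 2.2 / 2.2 | 1.00, 4.5% | 1.01, 4.7% |
| 2.0 / 2.1 | 0.96, 6.2% | 0.95, 5.3% |
| 1.8 / 2.0 | 0.93, 6.9% | 0.90, 7.9% |
| 1.4 / 1.8 | 0.84, 10.2% | 0.80, 11.7% |
| 2.6 / 2.4 | 1.11, 3.1% | 1.10, 2.9% |

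UN gave a mean TRC3 standard error of about 0.33 in every setting; its error rates rest on 150 runs and are too noisy to use. The heterogeneous structures were not fitted. By the formula, a TRC3-specific variance returns r to 1 and the error to 5%.

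**The case against.** The strongest reply is that harm needs two events together: UN must fail, and the variances must differ. UN has 6 parameters for 380 women, so failure is unlikely for OPP. That stands.

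A reader might infer that UN is likely to fail for dyspareunia (few scored days) or rescue tablets (many zeros). The documents do not support this. In simulated REML fits with assumed correlations and 10% dropout, 100 per setting, UN converged every time for a rescue-like endpoint with about 60% zeros, and every time for a dyspareunia-like endpoint with 70% or 50% of women reporting per cycle. It converged 98 times in 100 with only about 60 women per cycle. The optimiser was not PROC MIXED, so this is indicative only.

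The plan also has a partial safeguard. The TRC3-only ANCOVA uses TRC3 variance alone, and SAP 8.4.3 repeats it for DYS, NMPP, dyspareunia and rescue medication. Cycle-wise SDs of change are summarised (SAP 8.1.1, 8.3.5), so unequal variances would show. But the ANCOVA is supplementary and does not replace the primary interval, and SAP 8.5.3 states none for interference with daily activities.

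Finally, the protocol's amendment history records CS and AR(1) as added in agreement with the FDA. That is a reason to keep them as last resorts. It does not prevent trying less restrictive structures first.

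**Conclusion.** The point holds in conditional form. If UN fails and CS or AR(1) is used with model-based errors, the TRC3 interval is mis-sized unless the cycle variances are equal. Over the assumed range the error runs from about 3% (falling) through 5% (flat) to 6.5–9.2% (rising, 1.9/2.1 to 1.5/1.9), and to about 10% in the most extreme case tried.

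Three stronger readings are not supported:

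- That the planned primary test is anti-conservative: it is not if UN converges, which is the likely outcome.
- That the fallback produces false positives: the direction depends on SDs that the documents do not give.
- That the SAP prescribes model-based errors in the fallback: this is inferred from example code showing only the UN fit, and the SAP does not state the method for that branch.

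AR(1) is reached only if CS also fails, so CS is the fallback that matters in practice. This is a low-priority, cheap improvement; the sample size of 380 and the 84% power do not change.

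**What to change.** In SAP 8.3.5 and Table 2, and for every longitudinal endpoint, set the sequence on UN nonconvergence before unblinding:

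1. Refit UN with other starting values or optimiser settings.
2. Try TOEPH, ARH(1) and CSH in that order (5, 4 and 4 parameters for three cycles, against 6 for UN). Each keeps a separate variance per cycle.
3. Keep the protocol's CS and then AR(1) as last resorts, with a sandwich standard error and a named degrees-of-freedom method.

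Heterogeneous structures come before the sandwich because the analysis assumes data missing at random without imputation. A wrong covariance can then affect the TRC3 estimate as well as its standard error, and the sandwich repairs only the latter.

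Record the addition in SAP Section 10, which now reports no changes to the planned analyses.

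The cost is a few sentences. There are two downsides. Kenward-Roger cannot be combined with the sandwich, so the last-resort branch needs a simpler degrees-of-freedom method. The SAP would also add to the structures listed in the protocol (Synopsis, 9.4.2, 9.4.3).

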### 8.3.6. Sensitivity Analyses for the Primary Efficacy Endpoint

The following sensitivity analyses will be performed for the primary efficacy variable:

- The primary analysis will be repeated for the PP analysis set (sensitivity to analysis set).
- The primary analysis will be repeated, excluding cycles with <10 CCI NMPP scores or <2 CCI DYS scores (sensitivity to missing eCOA data).
- The primary analysis will be repeated, excluding the OPP score on days when prohibited pain medication was used (as reported in the eDiary) (sensitivity to effect of concomitant medication).

### 8.3.7. Supplementary Analyses for Primary Efficacy Endpoint

Two supplementary analyses will be performed for the MFAS, both using analysis of covariance (ANCOVA) models on the change from baseline to TRC3 with treatment as a fixed factor and baseline OPP as a covariate. In the first analysis, only subjects with data from TRC3 will be included. In the second analysis, subjects without data from TRC3 will have their TRC3 value imputed using last observation carried forward (i.e. the last available of the TRC2 and TRC1 values will be used.)

Estimated treatment differences (each OG-6219 treatment group versus Placebo) with corresponding 95% CI and 2-sided p-values will be derived from the model.

Analysis using an ANCOVA model will be implemented using the SAS® procedure MIXED as follows (example code only):

```
PROC MIXED DATA = ...;  
  CLASS TREATMENT;  
  MODEL CHG = BASELINE TREATMENT;  
  LSMEANS TREATMENT / PDIFF CL;  
RUN;
```

where CHG = change from baseline to TRC3

TREATMENT = randomized treatment group (CCI BID, CCI BID, CCI BID, and placebo)

BASELINE = baseline cycle value

## 8.4. Analyses Supporting Secondary Efficacy Objectives

### 8.4.1. Secondary Efficacy Endpoints

#### ENDOMETRIOSIS-RELATED PAIN (DYS, NMPP, AND DYSPAREUNIA) SCORES

The secondary efficacy variables of endometriosis-related pain scores are:

- Change from BC to TRC3 in the mean DYS score
- Change from BC to TRC3 in the mean NMPP score
- Change from BC to TRC3 in the mean dyspareunia score

The mean DYS and mean NMPP scores will be calculated similar to the mean OPP score.

The mean DYS score will be calculated for each cycle as the total of CCI DYS scores reported during the cycle divided by the number of days during the cycle when a DYS score was reported. The mean NMPP score will be calculated for each cycle as the total of CCI NMPP scores reported during the cycle divided by the number of days during the cycle when a NMPP score was reported.

The mean dyspareunia score will be calculated for each cycle as the total of dyspareunia scores reported during each cycle divided by the number of days when participants engaged in any sexual activity that involved full vaginal penetration during each cycle (i.e., the number of days during the baseline cycle when a dyspareunia score was reported).

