**Table 1: Objectives and Endpoints (as described in the study protocol)**

Objectives	Endpoints
Primary Endpoints The following primary efficacy endpoint will be assessed comparing Group A (CCI BID), B (CCI BID), C (CCI BID) with Group D (Placebo)	

 
To evaluate the efficacy of 3 dose levels of OG-6219 (Group A, B, C) versus Placebo (Group D) in reducing OPP during TRC3, as measured by a NRS in the eDiary
 
	
 
Change from BC to TRC3 in the mean OPP scorea
 

The following primary safety endpoints will be assessed for Group A (CCI BID), B (CCI BID), C (CCI BID) and Group D (Placebo)	

 
To evaluate the safety and tolerability of OG-6219
 
	
 
Proportion of participants who experienced any AEs/SAEs
 
Abnormalities in clinical laboratory assessments, vital signs, and physical examination
 
Proportion of participants who prematurely discontinued study treatment due to AEs/SAEs
 

Secondary Efficacy Endpoints The following secondary endpoints will be assessed comparing Group A (CCI BID), B (CCI BID), C (CCI BID) with Group D (Placebo)	
1. To evaluate the efficacy of 3 dose levels of OG-6219 (Groups A, B, C) versus Placebo (Group	
 
Change from BC to TRC3 in the mean DYS score
 

D) in reducing DYS during TRC3, as measured by a NRS in the eDiary	
2. To evaluate the efficacy of 3 dose levels of OG-6219 (Groups A, B, C) versus Placebo (Group D) in reducing NMPP during TRC3, as measured by a NRS in the eDiary	
 
Change from BC to TRC3 in the mean NMPP score
 

3. To evaluate the efficacy of 3 dose levels of OG-6219 (Group A, B, C) versus Placebo (Group D) reducing dyspareunia during TRC3, as measured by a NRS in the eDiary	
 
Change from BC to TRC3 in the mean dyspareunia score
 

4. To evaluate the daily use of Sponsor provided rescue medication taken for ERP at TRC1, TRC2, and TRC3	
 
Change from BC to TRC1, TRC2, and TRC3 in the mean number of tablets of rescue medication for ERP
 
Change from BC to TRC1, TRC2, and TRC3 in the proportion of days participant has used rescue medication for ERP
 

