### 8.3. Analyses Supporting Primary Efficacy Objective

#### 8.3.1. Efficacy assessments

Participants will complete the efficacy assessments in the **CCI** eDiary in the order presented

below:

- Vaginal bleeding pattern
- Endometriosis-related pain NRS for OPP (including vaginal bleeding)
- Dyspareunia
- Interference with daily activities
- Rescue medication use and number of tablets
- Prohibited pain medication use and reason

HRQoL and Productivity Questionnaires are conducted at Study visits per SoA:

- PGI-S
- PGI-C
- EHP-30
- WPAI-Endometriosis
- PROMIS Fatigue Short Form 6a
- EQ-5D-5L

Participants will complete eDiary items **CCI** asking about the severity of their worst pain over the last 24 hours on 11-point NRS for endometriosis-related pain. Endometriosis-related pain severity will be provided based upon an NRS from 0 (no pain) to 10 (worst pain imaginable) where lower value represents a better outcome.

**CCI** DYS is defined as the NRS endometriosis-related pain severity entered on a menstrual bleeding day, and **CCI** NMPP is defined as the NRS endometriosis-related pain severity entered on a non-menstrual bleeding day. **CCI** OPP is defined as the NRS endometriosis-related pain severity entered on any day regardless of menstrual bleeding (i.e. one cycle of **CCI** OPP scores consists of **CCI** DYS scores and **CCI** NMPP scores for the cycle).

The definition for a menstrual bleeding day used in the determinations for **CCI** DYS and **CCI** NMPP will be based upon bleeding information collected from the **CCI** diary for the two questions below:

- (1a) During the past 24 h did you have any vaginal bleeding or spotting?

- (1b) During the past 24 h have you been on your period?

If both questions are answered “Yes”, then that day qualifies as a menstrual bleeding day and the pain score is DYS. If either question is answered “No”, then that day is a non-menstrual bleeding day and the pain score is NMPP. OPP score is defined as DYS for menstrual bleeding days and as NMPP for non-menstrual bleeding days.

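### The SAP states the denominator of the mean dyspareunia score in two incompatible ways in one sentence; taken literally, one of them gives treatment-cycle values that are not means.

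*SAP*

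**What the plan says.** The third secondary efficacy endpoint is "Change from BC to TRC3 in the mean dyspareunia score" (SAP Table 1 and 8.4.1). SAP 8.4.1 derives the cycle value in one long sentence with three parts:

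- Numerator: "The mean dyspareunia score will be calculated for each cycle as the total of dyspareunia scores reported during each cycle".
- Denominator, main clause: "divided by the number of days when participants engaged in any sexual activity that involved full vaginal penetration during each cycle".
- Denominator, closing parenthesis: "i.e., the number of days during the baseline cycle when a dyspareunia score was reported".

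Just above, the same section defines the dysmenorrhea (DYS) mean with a denominator from its own cycle: "divided by the number of days during the cycle when a DYS score was reported". The definitions for non-menstrual pelvic pain (NMPP) and rescue medication (SAP 8.4.1), overall pelvic pain (OPP; SAP 8.3.3, Protocol 9.4.2) and interference with daily activities (SAP 8.5.1) follow the same pattern. The visible protocol text names the dyspareunia endpoint but gives no formula for it.

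The cycle values feed the longitudinal model, both supplementary ANCOVAs (one with last observation carried forward) and the per-protocol sensitivity analysis (SAP 8.4.3).

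**The concern.** A parenthesis that begins with i.e. tells the programmer what to count. Here it names days with a score in the baseline cycle, whichever cycle is being averaged. For treatment cycles 1 to 3 that divides one cycle's total by another cycle's count, and the result is not an average. It also conflicts with the main clause, which counts within each cycle.

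At stake is what the endpoint measures. Under the literal parenthesis, a woman with unchanged pain who has intercourse less often appears to improve, and one who has it more often, which could itself be a benefit, appears to worsen. A treatment cycle cut short by stopping treatment is affected in the same way: days after the last dose are left out of that cycle (SAP 8.3.3.1), so its total shrinks while the baseline count stays fixed.

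None of the planned analyses would expose the problem, because all of them start from the same derived cycle value. The minimum-count sensitivity analyses specified for DYS and NMPP are not specified for dyspareunia (SAP 8.4.3). The rule requiring at least one score in the cycle is stated for OPP (SAP 8.3.3) and, by reference, for DYS and NMPP, but not for dyspareunia.

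**Working it through.** The plan gives no figure for this derivation, so there is none to reproduce. The check compares the two denominators algebraically and then with numbers.

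**Inputs**

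- Numerator and both denominators: SAP 8.4.1, as quoted above.
- Scale: Table 1 of the SAP says only "reducing dyspareunia during TRC3, as measured by a NRS in the eDiary". The range is given for endometriosis-related pain in SAP 8.3.1: "Endometriosis-related pain severity will be provided based upon an NRS from 0 (no pain) to 10 (worst pain imaginable". Applying 0 to 10 to dyspareunia is an assumption.
- Scored days per cycle: not given in the documents. Counts from 0 to 8 are assumed for illustration, with a constant score within each example.

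**Formulas**

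Let S be the total score in a treatment cycle, n the number of scored days in that cycle, n_BC the number of scored days in the baseline cycle, and m = S/n the true cycle mean.

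- Same-cycle denominator: S/n = m.
- Literal parenthesis: S/n_BC = m × (n/n_BC).
- Error in the cycle value, and so in the change from BC: m × (n/n_BC − 1).
- The literal value exceeds 10 when n/n_BC > 10/m. For m = 6 this needs a ratio above 10/6 = 1.67; for m = 5, above 2.

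The BC value is the same under both rules, because there n = n_BC.

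**Results**

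| Scored days in BC | Scored days in TRC3 | Score each day | Same-cycle TRC3 value | Literal TRC3 value | Error in change from BC |
|---|---|---|---|---|---|
| 4 | 4 | 6 | 6.0 | 24/4 = 6.0 | 0.0 |
| 8 | 4 | 6 | 6.0 | 24/8 = 3.0 | −3.0 (false improvement) |
| 4 | 2 | 6 | 6.0 | 12/4 = 3.0 | −3.0 (false improvement) |
| 4 | 8 | 6 | 6.0 | 48/4 = 12.0 | +6.0 (false worsening, off the scale) |
| 2 | 5 | 5 | 5.0 | 25/2 = 12.5 | +7.5 (false worsening, off the scale) |
| 4 | 0 | none | missing | 0/4 = 0 if an empty sum counts as 0 | apparent full relief where the value should be missing |

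With no scored day in BC, the change from BC cannot be formed under either rule.

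**Effect on the comparison between arms**

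If the ratio n/n_BC is unrelated to pain and distributed alike in all arms, the literal rule multiplies the treatment difference by the average ratio and adds noise. If the ratio differs between arms, for example because less pain leads to more intercourse, the comparison is biased, in that example against the effective dose.

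**The case against.** The strongest reply is that the intended meaning is recoverable. The main clause is correct: it takes each cycle's scores and divides by that cycle's activity days. Every parallel cycle average in the SAP uses its own cycle's count, and the quantity is called a mean throughout. SAP 8.2.3 lists the mean dyspareunia score among the baseline-cycle characteristics, so baseline wording may simply have been carried over, though that is inference. A programmer would have to override the main clause and the parallel definitions to produce the errors shown above.

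Most of this stands. A reader might infer that the SAP defines every cycle's dyspareunia mean with the baseline count, and hence that the treatment-cycle means are wrong. The documents do not support that: they contain two incompatible rules, and nothing shows which one was programmed. Nor do they support a flat statement that the score can exceed 10. That requires literal programming, a sufficiently large ratio of day counts, and a 0 to 10 range that the visible text does not state for this item.

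What does not stand is that the text can be left alone. A SAP is meant to fix derivations before unblinding, and for treatment cycles 1 to 3 no reading reconciles the parenthesis with a within-cycle mean. The two clauses differ in a second respect too: one counts activity days and the other counts scored days, and these need not be equal.

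**Conclusion.** The concern holds as an internal contradiction in the derivation of one secondary efficacy endpoint. Under the literal parenthesis, the treatment-cycle value is the true mean times n/n_BC. The error is zero when day counts are equal and runs to several points on the score when they differ by a factor of two. That proportional distortion follows from the formula and does not depend on the scale's range. The point values in the table rest on assumed day counts and constant scores, and the off-scale results also on the assumed 0 to 10 range.

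Severity: should-fix. The OPP primary endpoint, the sample size, DYS, NMPP and the safety analyses are unaffected. P-values are nominal with no multiplicity adjustment (SAP 8.1.7), so no testing hierarchy is disturbed. Confidence is high that the sentence contradicts itself; whether any result would be wrong depends on the program, which the documents do not show.

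**What to change.** In the parenthesis of SAP 8.4.1, replace the reference to the baseline cycle by a reference to that cycle, so that the denominator is the number of days in the same cycle with a dyspareunia score. Make the main clause agree by saying that activity days without a score are not counted. Add that the cycle mean is missing when the cycle has no dyspareunia score, so that an empty cycle cannot enter as zero. Then check that the derivation program follows this rule.

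The cost is one changed phrase, two short clarifications and one program check. No new data or additional analyses are needed.
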